### **8.1.2. Calculation of the Summary Statistics**

For continuous data the following rules will be applied:

- Missing values will not be imputed, unless specifically stated otherwise.
- Unrounded data will be used in the calculation of summary statistics.
- If the number of subjects with valid observations (n) <3, summary statistics will not be calculated, with the exception of n, minimum, and maximum.

- In general, as discontinuation data are not associated with any scheduled timepoint, they will be excluded from all calculations of summary statistics and statistical analyses. Exceptions may be made where justified.

For categorical data the following rules will be applied:

- For ordered categorical data (eg, AE severity), all categories between the possible minimum and maximum categories will be included, even if  $n = 0$  for a given category.
- For non-ordered categorical data (eg, race), only those categories for which there is at least 1 subject represented will be included; unless specifically stated otherwise.
- Missing values will not be imputed, unless specifically stated otherwise. A ‘missing’ category will be included for any parameter for which information is missing. This will ensure that the population size totals are consistent across different parameters.

### **8.1.3. Triplicate Readings**

For vital signs data only, where triplicate readings are taken, the median of triplicate readings will replace the separate individual triplicate readings in all calculations.

For 12-lead ECG data only, where triplicate readings are taken, the mean of triplicate readings will replace the separate individual triplicate readings in all calculations.

In case of incomplete triplicate readings (eg, only 2 out of 3 readings were recorded), the mean and/or medians will be calculated, as appropriate, based on the number of readings available.

### **8.1.4. Repeat and Unscheduled Readings**

For vital signs and 12-lead ECG data only, any predose value recorded in addition to the original value or a postdose value recorded within 15 minutes of the original value will be defined as a repeat value; any postdose value recorded more than 15 minutes after the original value will be defined as an unscheduled value. For all other data types (eg, laboratory parameters), any value recorded in addition to the original value will be defined as an unscheduled value.

The original value will be replaced by the last associated repeat value in all calculations, with the exception of the 12-lead ECG outlier analysis (see [Section 8.6.4](#)).

As unscheduled values are not associated with any scheduled timepoint, they will be excluded from all calculations, with the exception of the baseline derivation (see [Section 8.1.5](#)) and 12-lead ECG outlier analysis (see [Section 8.6.4](#)).

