7.2.3. Vital Signs

Supine blood pressure, supine pulse rate, respiratory rate, and oral body temperature will be assessed at the times indicated in the Schedule of Assessments in [Appendix 6](#). Vital signs may also be performed at other times if judged to be clinically appropriate or if the ongoing review of the data suggests a more detailed assessment of vital signs is required.

Day 1 predose blood pressure, pulse rate, and respiratory rate will be measured in triplicate at approximately 2-minute intervals. All subsequent measurements will be performed singly and repeated once if outside the relevant clinical reference ranges. Oral body temperature will be measured singly.

Subjects must be supine for at least 5 minutes before blood pressure and pulse rate measurements.

In the event orthostatic measurements are required (if deemed clinically appropriate by an investigator or designee), the supine blood pressure and pulse rate will be measured after the subject has been supine for at least 5 minutes. The subject will then stand for at least 2 minutes and the standing blood pressure and pulse rate will be measured.

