7.2.4. Electrocardiogram

7.2.4.1. 12-lead Electrocardiogram

Resting 12-lead ECGs will be recorded after the subject has been supine and at rest for at least 5 minutes at the times indicated in the Schedule of Assessments in [Appendix 6](#). Single 12-lead ECGs will be repeated once if either of the following criteria apply:

- QTcF value > 500 ms
- QTcF change from the baseline (predose) is > 60 ms.

Additional 12-lead ECGs may be performed at other times if judged to be clinically appropriate or if the ongoing review of the data suggests a more detailed assessment of ECGs is required. The investigator (or designee) will perform a clinical assessment of each 12-lead ECG.

Day 1 predose 12-lead ECGs will be measured in triplicate at approximately 2-minute intervals. All subsequent measurements will be performed singly and repeated once if outside the relevant clinical reference ranges.

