# **8. STATISTICAL METHODOLOGY**

## **8.1. General**

Listings will be provided for all data captured in the database, with the exception of medical history. Listings will include all subjects assigned to the all subjects population and include data up to the point of study completion or discontinuation. Subjects are generally considered to have completed the study if they complete the scheduled follow-up visit (rather than early termination visit). Any subject who discontinues the study will be identified accordingly in the listings. Summaries will include the subjects assigned to the relevant population based on data type.

Data analysis will be performed using the SAS® statistical software package Version 9.4 (or higher if a new version is issued during the study).

Analysis Data Model (ADaM) datasets will be prepared using Clinical Data Interchange Standards Consortium (CDISC) ADaM Version 2.1 (or higher if a new version is issued during the study) and CDISC ADaM Implementation Guide Version 1.1 (or higher if a new version is issued during the study). Pinnacle 21 Community Validator Version 4.0.1 (or higher if a new version is issued during the study) will be utilised to ensure compliance with CDISC standards.

For all statistical analyses, the hypothesis testing will be 2-sided and carried out on 0.05 significance level, unless specifically stated otherwise.

Caution should be used when interpreting results from the statistical analyses conducted in this study because the sample size is not based on power calculations.

Where reference is made to 'valid' data, this refers to non-missing data which meet the predetermined criteria (eg, are not flagged for exclusion).

Where reference is made to 'all calculations', this includes, but is not limited to, summary statistics, statistical analyses, baseline derivation, and changes from baseline.

All figures will be produced on linear-linear or discrete-linear scales, as applicable, unless specifically stated otherwise.

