#### **8.6.3. Vital Signs Parameters**

All vital signs parameters and their changes from baseline will be listed, as applicable; any value outside the clinical reference range will be flagged.

Summary tables and boxplots by treatment and timepoint will be provided for all vital signs parameters and their changes from baseline, as applicable.

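### Repeats prompted by abnormal post-dose vital signs and ECGs replace the original in by-timepoint summaries, pulling them toward normal; vital signs and non-QTc ECG parameters have no summary that keeps the original

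*SAP*

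**What the plan says.** **When a repeat is taken.** For vital signs after the Day 1 predose triplicate, protocol 7.2.3 says: "All subsequent measurements will be performed singly and repeated once if outside the relevant clinical reference ranges". Protocol 7.2.4.1 applies the same rule to ECGs and adds two triggers, QTcF above 500 ms or a change from baseline above 60 ms: "Single 12-lead ECGs will be repeated once if either of the following criteria apply". Both sections also allow extra measurements when clinically appropriate. Neither gives a time for the repeat.

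**What the SAP does with it.** Section 8.1.4 says that, for vital signs and 12-lead ECG, "a postdose value recorded within 15 minutes of the original value will be defined as a repeat value", whereas "any postdose value recorded more than 15 minutes after the original value will be defined as an unscheduled value". The replacement rule is: "The original value will be replaced by the last associated repeat value in all calculations, with the exception of the 12-lead ECG outlier analysis". Section 8.1 defines the scope of all calculations: "this includes, but is not limited to, summary statistics, statistical analyses, baseline derivation, and changes from baseline". For later values: "As unscheduled values are not associated with any scheduled timepoint, they will be excluded from all calculations", apart from the baseline derivation and the ECG outlier analysis.

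**Which outputs are involved.** For vital signs, SAP 8.6.3 provides: "Summary tables and boxplots by treatment and timepoint will be provided for all vital signs parameters and their changes from baseline, as applicable". It has no outlier or categorical table. SAP 8.6.4 provides the same outputs for ECG parameters, plus an outlier analysis of QTcB and QTcF that uses every original, repeat and unscheduled post-dose value. Additional laboratory values are always unscheduled. Section 8.1 lists all captured data except medical history, and out-of-range values are flagged.

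**The concern.** Planned repeats are prompted by an abnormal first reading, while an in-range reading normally gets none. Replacing the first reading with the repeat therefore applies a correction to one part of the distribution only. High readings are partly high by chance, so the repeat tends to be lower; for low readings it tends to be higher. Either way the tabulated value moves toward the reference range.

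Vital signs and 12-lead ECG parameters are primary safety endpoints, and no inferential safety analysis is planned, so the descriptive tables carry the reported result. If the drug shifts a parameter, more active than placebo readings cross the limit and are replaced, which shrinks the visible effect. For QTc the outlier table offsets this. For blood pressure, pulse, respiratory rate, temperature and ECG parameters such as PR and QRS, an out-of-range original that has been replaced appears only in a listing.

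**Working it through.** The plan states no figure on this point, so there is none to reproduce. The check covers applicability, direction and size.

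**Applicability.** The protocol supplied is version 5. The SAP is written to version 4 and says version 5 was never used. The version 4 to 5 change summary lists no change to 7.2.3 or 7.2.4, so the repeat rules are taken to apply.

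**Inputs.** From the documents: the repeat trigger, the 15-minute definition and the replacement rule. Assumed: systolic limits 90 and 140 mmHg (140 is borrowed from exclusion criterion 5, which is an eligibility limit; 90 has no source, and that criterion's lower limit is 80); true baseline mean 120; between/within-subject SD 8/5, 10/7 and 10/10; repeat error independent of the original error; baseline unbiased.

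**Formula.** Let the original be x = t + e, with true value t ~ N(m, b²), error e ~ N(0, w²) and s = √(b² + w²). If an out-of-range x is replaced by a second reading of the same t, then

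bias in the mean = -(w²/s)·[φ((140 - m)/s) - φ((m - 90)/s)],

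where φ is the standard normal density.

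**True rise of 10 mmHg (m = 130):**
- SD 8/5: s = 9.43, w²/s = 2.65, φ(1.06) = 0.2275, lower term negligible. Bias -0.60; tabulated 9.4.
- SD 10/7: s = 12.21, w²/s = 4.01, φ(0.819) = 0.2852, lower φ = 0.0019. Bias -1.14; tabulated 8.9.
- SD 10/10: s = 14.14, w²/s = 7.07, φ(0.707) = 0.3107, lower φ = 0.0073. Bias -2.15; tabulated 7.9.

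**No drug effect (m = 120):**
- SD 8/5: -2.65 × (0.0422 - 0.0025) = -0.1.
- SD 10/7: -4.01 × (0.1042 - 0.0195) = -0.3.
- SD 10/10: -7.07 × (0.1468 - 0.0421) = -0.7.

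Simulation with 2,000,000 draws per scenario agrees: 9.39, 8.86 and 7.86 for the rise; -0.09, -0.35 and -0.75 with no effect.

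**Active minus placebo.** Placebo values are pulled down slightly too, so the contrast loses less than the active mean: 9.40 + 0.10 = 9.5, 8.86 + 0.34 = 9.2 and 7.86 + 0.74 = 8.6, against a true 10.

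**Repeat timing.** If half the repeats fall within 15 minutes, the bias halves and the rise is tabulated as 9.7, 9.4 and 8.9.

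**Share of values out of range, true rise of 10 mmHg.** Under the same model the true value lies above 140 with probability P(Z > 10/b).

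| SD (between/within) | Original readings | After replacement | True value above 140 |
|---|---|---|---|
| 8/5 | 14.5% | 7.7% | 10.6% |
| 10/7 | 20.7% | 11.3% | 15.9% |
| 10/10 | 24.2% | 11.3% | 15.9% |

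Single originals overstate the share of subjects truly above the limit, and replacement understates it.

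**QTcF in by-timepoint tables.** Assuming an upper limit of 450 ms, mean 405 and SD 15/8 or 18/10, a true rise of 20 ms is tabulated as 19.5 or 19.1 ms. With no effect the bias is -0.04 to -0.18 ms.

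**The case against.** The strongest reply is that a confirmatory repeat is a coherent convention. A first reading spoiled by cuff or movement artefact is better replaced, and a sustained drug effect would usually recur minutes later. Groups have only 6 or 8 active subjects, so one assumed 30 mmHg artefact left in place moves a group mean by 30/6 = 5 or 30/8 = 3.75 mmHg, more than the bias calculated above. The rule is the same in both arms, no safety test depends on it, escalation rests on the investigator's review of all available data, and the specified stopping criteria use no vital sign or ECG mean.

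This stands as a limit on size and consequence. It does not remove the direction of the bias or supply a table that keeps the original.

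A reader might also infer several stronger things that the documents do not support:
- *That abnormal readings vanish from every safety output.* The QTcB/QTcF categories use all readings, laboratory re-measurements do not displace originals, adverse event summaries are not involved, and listings retain and flag originals.
- *That only out-of-range readings can be replaced.* An ECG can be repeated for a change above 60 ms, and any extra reading within 15 minutes replaces the original, whatever prompted it.
- *That every repeat replaces.* A post-dose value taken after more than 15 minutes does not.
- *That each exceedance removed is lost signal.* For a subject whose true systolic pressure is 135, a reading above an assumed limit of 140 is a false exceedance, and replacing it removes noise.
- *That laboratory data are handled inconsistently.* A later sample is a new specimen, so a different rule is defensible.

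**Conclusion.** The point holds for by-timepoint summaries, changes from baseline and boxplots of vital signs and 12-lead ECG parameters. Following the plan exactly biases them toward normal and attenuates a real drug effect; with no effect it creates no difference between arms. It matters most for vital signs and non-QTc ECG parameters.

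Confidence is high on direction and low on size. On the assumed systolic inputs, the loss from a true 10 mmHg rise is about 0.6 to 2.1 mmHg, or about half that if only half the repeats qualify. A different reference range, smaller measurement error, correlated errors or artefact in first readings would all change these figures. The effect on the share of out-of-range values is larger than on the mean, though part of that reduction is noise. The change is worth making because it is cheap and concerns primary safety endpoints; it does not undermine the safety assessment as a whole.

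**What to change.** 1. In SAP 8.6.3, add a by-treatment table of each subject's maximum and minimum post-dose value and maximum change from baseline for each vital sign. Use all original, repeat and unscheduled values, as 8.6.4 does for QTc. This is the main change.
2. In SAP 8.1.4, use the original scheduled post-dose value in by-timepoint summaries of vital signs and ECG unless a technical error in the original is documented in source. This also covers the non-QTc ECG parameters.
3. The 15-minute definition may stay as a label separating repeats from unscheduled values, but it should not decide which value is tabulated. Removing it altogether would be a matter of convention and is not needed.

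Cost: SAP wording, one extra table and its shell, with no new data. SAP section 1 allows supplementary analyses identified in the study report, so the table can be added even though the SAP is final. The downside is that an artefact not documented as a technical error would stay in the mean of a group of 6 or 8 active subjects. Averaging original and repeat is a middle course that roughly halves the bias (9.7, 9.4 and 8.9 for the 10 mmHg rise), but it still depends on the outcome.

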### **8.1.5. Definitions of Baseline and Change from Baseline**

The baseline will be defined as the last value recorded prior to the first dose. If the date/time of the value is incomplete or missing, it will be excluded from the baseline calculation, unless the incomplete date/time indicates the value was recorded prior to the first dose.

Individual changes from baseline will be calculated by subtracting the individual subject's baseline value from the value at the postdose timepoint.

The summary statistics for change from baseline will be derived from individual subjects' values (eg, mean change from baseline will be the mean of the individual changes from baseline for all subjects, rather than difference between the mean value at the postdose timepoint and mean value at baseline).

See [Section 8.1.4](#) for more detail on handling repeat and unscheduled readings in the calculations. See [Section 8.1.3](#) for more detail on handling of triplicate readings in the calculations.

## **8.2. Subject Disposition and Population Assignment**

Subject disposition and population assignment will be listed.

A summary table by treatment will be provided, based on the safety population.

## **8.3. Screening Demographics**

The screening demographics including age, sex, race, ethnicity, height, body weight, and body mass index will be listed.

A summary table by treatment will be provided, based on the safety population.

## **8.4. Prior and Concomitant Medication**

Prior medication will be defined as medication that ends prior to the first dose. Concomitant medication will be defined as medication that starts during or after the first dose or starts but does not end prior to the first dose.

Prior and concomitant medications will be coded using the World Health Organization Drug Dictionary (WHODrug) Global, Format B3, Version March 2021 (or later if a new version is issued during the study; see the data management plan [DMP] for more details). Prior and concomitant medications will be listed.

## 8.5. Pharmacokinetic Assessments

### 8.5.1. Pharmacokinetic Analysis

The following PK parameters will be determined where possible from the plasma and urine concentrations of NST-6179 using noncompartmental methods in validated software program Phoenix WinNonlin (Certara, Version 8.1 or higher):

#### Part A - SAD

Parameter	Units a	Definition
Plasma PK Parameters		
AUC 0-tlast	h*ng/mL	area under the concentration-time curve from time 0 to the time of the last quantifiable concentration (t last ) b
AUC 0-∞	h*ng/mL	area under the concentration-time curve from time 0 extrapolated to infinity c
AUC 0-24	h*ng/mL	area under the concentration-time curve from time 0 to 24 hours postdose
AUC 0-72	h*ng/mL	area under the concentration-time curve from time 0 to 72 hours postdose (for calculation of CL R )
%AUC extrap	%	percentage of area under the concentration-time curve due to extrapolation from the last quantifiable concentration to infinity
C max	ng/mL	maximum observed concentration
t max	h	time of the maximum observed concentration
t last	h	time of the last quantifiable concentration
t 1/2	h	apparent terminal elimination half-life
CL/F	L/h	apparent total clearance
V z /F	L	apparent volume of distribution during the terminal phase
DAUC 0-tlast	h*ng/mL/mg	AUC 0-tlast normalised by dose administered d
DAUC 0-∞	h*ng/mL/mg	AUC 0-∞ normalised by dose administered d
DC max	ng/mL/mg	C max normalised by dose administered d
Urine PK Parameters		
Ae t1-t2	mg	amount of the dose administered recovered over the time interval t 1 to t 2 , calculated for each interval from the start of the collection interval and from the start of the dosing interval (time 0)
fe t1-t2	%	percentage of the dose administered recovered over the time interval t 1 to t 2 , calculated for each interval from the start of the collection interval and from the start of the dosing interval (time 0)
CL R	L/h	renal clearance, calculated as Ae 0-72 /AUC 0-72 or other appropriate collection interval

a Units are based on concentration units (provided by the bioanalytical lab or preferred units for presentation of PK parameters) and dose units used in the study.

b The AUC will be calculated using the linear trapezoidal rule for increasing concentrations and the logarithmic rule for decreasing concentrations (linear up/log down rule).

c Based on the last observed quantifiable concentration

d Calculated by dividing the parameter by the dose (mg)

**Part B - MAD**

Parameter	Units a	Definition
Plasma PK Parameters		
AUC 0-<math>\tau</math>	h*ng/mL	area under the concentration-time curve over a dosing interval, may be referred to AUC 0-24 for Day 1 b
AUC 0-<math>\infty</math>	h*ng/mL	area under the concentration-time curve from time 0 extrapolated to infinity c (Day 1 only)
%AUC extrap	%	percentage of area under the concentration-time curve due to extrapolation from the last quantifiable concentration to infinity (Day 1 only)
C max	ng/mL	maximum observed concentration
C min	ng/mL	minimum observed concentration in a dosing interval (Day 14 only)
t max	h	time of the maximum observed concentration
t last	h	time of the last quantifiable concentration
t 1/2	h	apparent terminal elimination half-life
CL/F	L/h	apparent total clearance
V z/F	L	apparent volume of distribution during the terminal phase
RA AUC0-<math>\tau</math>	NA	observed accumulation ratio based on AUC 0-<math>\tau</math>
RA Cmax	NA	observed accumulation ratio based on C max
DAUC 0-<math>\tau</math>	h*ng/mL/mg	AUC 0-<math>\tau</math> normalised by dose administered d
DAUC 0-<math>\infty</math>	h*ng/mL/mg	AUC 0-<math>\infty</math> normalised by dose administered d (Day 1 only)
DC max	ng/mL/mg	C max normalised by dose administered d
Urine PK Parameters		
Ae t1-t2	mg	amount of the dose administered recovered over the time interval t 1 to t 2 , calculated for each interval from the start of the collection interval and from the start of the dosing interval (time 0)
fe t1-t2	%	percentage of the dose administered recovered over the time interval t 1 to t 2 , calculated for each interval from the start of the collection interval and from the start of the dosing interval (time 0)
CL R	L/h	renal clearance, calculated as Ae/AUC using matched collection intervals; at steady state, collection intervals will be matched to the dosing interval

a Units are based on concentration units (provided by the bioanalytical lab or preferred units for presentation of PK parameters) and dose units used in the study.

b The AUC will be calculated using the linear trapezoidal rule for increasing concentrations and the logarithmic rule for decreasing concentrations (linear up/log down rule).

c Based on the last observed quantifiable concentration

d Calculated by dividing the parameter by the dose (mg)

Additional PK parameters may be determined where appropriate.

The PK analysis will be carried out where possible using actual dose administered (mg) and actual postdose blood sampling times. If an actual time is missing, the sample concentration result will be treated as missing unless there is scientific justification to include the result using the nominal time.

The parameters  $C_{\max}$ ,  $C_{\min}$ , and  $t_{\max}$  will be obtained directly from the concentration-time profiles. If  $C_{\max}$  occurs at more than 1 timepoint,  $t_{\max}$  will be assigned to the first occurrence of  $C_{\max}$ .

The accumulation ratio(s) (RAAUC0-τ and RACmax) will be calculated as follows:

$$RA_{AUC_{0-\tau}} = AUC_{0-\tau} \text{ profile day 14} / AUC_{0-\tau} \text{ profile day 1}$$

$$RA_{C_{\max}} = C_{\max} \text{ profile day 14} / C_{\max} \text{ profile day 1}$$

The parameter AUC0-tlast or other common partial area may be used to determine RAAUC0-τ if AUC0-τ cannot be reliably calculated for the majority of subjects.

